4.2.1 Disposition of subjects

The number and percentage of subjects who were enrolled to the study, received treatment, enrolled and did not receive treatment, completed treatment, discontinued prematurely from treatment, completed the study, withdrew from the study, and reasons for withdrawal from the study will be summarized for all subjects.

The number and percentage of subjects in each analysis set, and in each center (using SAS) will also be presented.

4.2.2 Protocol deviations

Important protocol deviations are defined in Section 2.2 and will be listed for all subjects received study treatment.

The number and percentage of subjects with any IPD will be summarized for each IPD category. Subjects with more than one deviation in the same IPD category will be counted once for that IPD category. Any subjects who have deviations in more than one IPD category will be counted once in the overall summary.

4.2.3 Demographic and other baseline characteristics

Demographic and other baseline characteristics will be listed for all subjects in SAS using the rules for summarizing continuous and categorical variables described in Section 4.1.

In addition to being summarized as continuous variables, age, weight, and BMI will be summarized as the following categorical variable: age group ($<65, \ge65$ years, as well as categories of $<20, \ge20$ - $<35, \ge35$ - $<50, \ge50$ - $<65, \ge65$ - $<75, \ge75$ years.), weight group ($<70, \ge70$ - $\le90, >90$ kg) and BMI group (underweight [<18.5], normal [18.5 - <25.0], overweight [25.0 - <30.0] and obese [>=30.0].

The number and percentage of subjects with comorbidities will also be presented, as well as the number of comorbidities (e.g. the number and percentage of subjects with 1, 2, 3, etc. comorbidities).

Medical history and surgical history are coded using MedDRA (version 23.0) and will be summarized by System Organ Class (SOC) and Preferred Term (PT).

4.2.4 Prior and concomitant medications or procedures

The following summaries will be produced for all subjects in SAS:

- Summary of prior medications or procedures
- Summary of concomitant medications or procedures

All concomitant and other treatment data will be listed for all subjects in the SAS.

Missing coding terms should be listed and summarised as "Not coded".

4.3 Analysis of Pharmacokinetics

The PK analyses will be performed at AZ Research & Development.

The plasma concentrations of acalabrutinib and ACP-5862 will be listed for all subjects and summarized by analyte, and nominal sample time for all subjects in the PKS. Summary statistics, including sample size (n), arithmetic mean (Mean), standard deviation (SD), coefficient of variation (CV%), standard error of the mean (SEM), minimum, median, and maximum will be calculated for all nominal concentration timepoints.

Excluded subjects will be included in the concentration listings, but will be excluded from the summary statistics and noted as such in the tables.

All BLQ values will be presented as "BLQ" in the concentration listings and footnoted accordingly. For the calculation of summary statistics, plasma acalabrutinib and ACP-5862 concentrations BLQ will be treated as zero prior to the first quantifiable concentration and as missing elsewhere.

Mean and individual concentration-time profiles for plasma acalabrutinib and ACP-5862 will be presented on linear and semi-log scales. Linear mean plots will be presented with and without SD.

Plasma acalabrutinib and ACP-5862 PK parameters will be listed and summarized by analyte and treatment for all subjects in the PKS. Summary statistics (n, arithmetic mean, SD, CV%, SEM, minimum, median, maximum, geometric mean [Geom Mean] and geometric CV% [Geom CV%]) will be calculated for plasma acalabrutinib and ACP-5862 PK parameters. Excluded subjects will be listed in the PK parameter tables, but will be excluded from the summary statistics and noted as such in the tables.

Individual plasma concentrations of acalabrutinib and ACP-5862 will be presented with the same level of precision as received from the bioanalytical laboratory. Individual PK parameters will be reported to 3 significant figures for individual parameters, with the exception of T_{max} , T_{last} , and $t^{1}/_{2}$, which will be presented with 2 decimal places, and C_{max} , which will be presented in the same precision as the bioanalytical data.

The level of precision for each concentration and PK parameter statistic will be as follows:

- minimum/maximum with the same precision as in individual data
- arithmetic mean, median and geometric mean with one more level of precision than minimum/maximum
- SD with one more level of precision than mean/median
- n will be presented as an integer
- CV% and geometric CV% will be presented to 1 decimal place.

Potential correlations of exposure with safety and efficacy outcomes or biomarker measurements may be explored as warranted by the data.

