1.2 Study Design

Approximately 20 participants will be included to ensure at least 16 participants are evaluable. participants will receive acalabrutinib suspension (ie, acalabrutinib 100 mg suspension in COCA-COLA® delivered via NG tube) bid for 14 days (a maximum of 28 doses). In addition to receiving best supportive care (SOC).

To assess the effect of PPIs, all participants must be receiving treatment with a PPI at the start of the study. Treatment with a PPI can begin at any time prior to enrollment, provided participants have received PPI treatment for at least 24 hours prior to the first dose of acalabrutinib suspension. Any PPI is permitted, provided it meets the minimum equivalent daily dose of 20 mg rabeprazole. Participants must be on this dosage of PPI at the start of the study. They may be weaned off PPIs during the study if medically appropriate.

[figure not shown]
Blood samples for plasma PK assessment of acalabrutinib and its metabolite (ACP-5862) will be collected at pre-dose and 0.5, 1, 2, 4, 6, and 12 hours following treatment with acalabrutinib suspension as described in the table below. Note that the sample at 12 hours must be collected prior to the subsequent acalabrutinib dose (for trough PK sample).

Table 2 PK Visit and Description

PK Visit	Description	Rationale
PK Visit 1	First PK sampling will occur on Day 1 (ie, first dosing day for acalabrutinib suspension)	Allows an early assessment of acalabrutinib and ACP-5862 PK in participants receiving acalabrutinib suspension via NG tube
PK Visit 2	Second PK sampling will occur a minimum of 4 days after the start of PPI treatment, irrespective of the timing of NG tube placement and any time after 2 doses of acalabrutinib suspension have been given (ie, PK sampling can begin prior to the third dose, or anytime thereafter) PK Visit 2 can occur as early as Day 2 (if participant has been on a PPI for ≥ 4 consecutive days prior to receiving the third acalabrutinib dose), and up to Day 4 (if participant initiated PPI treatment 24 hours prior to receiving the first dose of acalabrutinib on Day 1)	PPI exposure must occur for 4 consecutive days to reach the maximum PPI on-target effect PK sample can commence at any point after the second dose of acalabrutinib suspension to ensure steady-state levels of the active metabolite and

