PK Visit 3	Third PK sampling will occur 3 days after PK Visit 2, OR on the last day the participant receives acalabrutinib treatment, whichever comes first	Allows an additional opportunity to assess the steady-state PK of acalabrutinib and ACP-5862 PK following delivery of acalabrutinib suspension via NG tube

Safety assessments, including AE reporting, will be performed through 28 (\pm 3) days after the last dose of the acalabrutinib suspension.

The study design is illustrated in Figure 1.

Blood samples for plasma PK assessment of acalabrutinib and its metabolite (ACP-5862) will be collected at pre-dose and 0.5, 1, 2, 4, 6, and 12 hours following treatment with acalabrutinib suspension. Note that the sample at 12 hours must be collected prior to the subsequent acalabrutinib dose (for trough PK sample).

Note: PK Visit 2 can occur as early as Day 2 (if participant has been on a PPI for \geq 4 consecutive days prior to receiving the third acalabrutinib dose), and up to Day 4 (if participant initiated PPI treatment 24 hours prior to receiving the first dose of acalabrutinib on Day 1). See table 3 for more information.

bid = twice daily; PK = pharmacokinetic(s); PPI = proton-pump inhibitor.

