 K_{el} will be calculated by log-linear regression of the terminal portion of the concentration-time profiles for the derivation of regression-based parameters where there are sufficient data. The AUCs will be calculated using 'Linear up/Log down' method. Where appropriate, the AUC_{last} will be extrapolated to infinity using Kel to obtain AUC_{inf}. The CL/F will be determined from the ratio of dose/AUC_{inf}. The Vz/F will be determined from the ratio of CL/F/Kel. The MR parameters will be calculated after molar conversion. If $t^1\!/_2$ is estimated over less than three half-lives, the Kel related values will be flagged in the data listings but will be excluded from summary and PK statistical analysis.

An Rsq adj value of ≥ 0.8 indicate good fit of the log-linear regression. Any Kel with a Rsq_adj of <0.8 be flagged in the data listings along with the regression-based parameters and discussed in the CSR. The Kel and related PK parameters will be excluded from summary and PK statistical analysis.

The minimum requirement for the calculation of AUCs will be the inclusion of at least 3 consecutive quantifiable concentrations. Where there are only 3 quantifiable concentrations at least one of these should follow the peak concentration. Where %AUC_{extrap} is >10%, AUC_{inf} and derived parameter values will be flagged and excluded from descriptive and inferential statistics and discussed in the CSR.

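### PK summaries name no PK visit, so as written first-dose and steady-state profiles share one cell; separately, and smaller, CL/F uses AUCinf at steady state

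*SAP*

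**What the plan says.** Section 1.2 and Table 2 of the SAP schedule three PK visits, each sampled pre-dose and at 0.5, 1, 2, 4, 6 and 12 h.

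- Visit 1 is on Day 1, with the first dose.
- Visit 2: "Second PK sampling will occur a minimum of 4 days after the start of PPI treatment", and after two doses of acalabrutinib. Part of the rationale is "to ensure steady-state levels of the active metabolite".
- Visit 3 is three days later or on the last treatment day, whichever comes first: "Allows an additional opportunity to assess the steady-state PK of acalabrutinib" and of the metabolite.

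Section 4.3 then sets the summaries. Concentrations are "summarized by analyte, and nominal sample time for all subjects in the PKS". For parameters, "PK parameters will be listed and summarized by analyte and treatment for all subjects in the PKS". The statistics include n, mean, SD, CV% and SEM, and for parameters also the geometric mean and geometric CV%. Values below the limit of quantitation before the first quantifiable concentration count as zero. No PK visit or PK day stratum is named in Section 4.3 or elsewhere in the SAP.

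For clearance, Section 3.1 states: "The CL/F will be determined from the ratio of" dose to AUCinf. Table 4 says the same and bases Vz/F on AUC0-inf. Neither distinguishes a first dose from steady state. Section 3.1 also excludes AUCinf and the parameters derived from it from the summaries when more than 10% of the AUC is extrapolated.

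**The concern.** The PK of acalabrutinib and ACP-5862 under a PPI is a primary objective, and Table 2 gives the visits different purposes. All participants receive the same treatment, so grouping by treatment separates nothing, and the nominal hours are identical at each visit. A programmer who follows Section 4.3 literally would put every profile of a subject into one cell. The mean would then describe neither the first dose nor steady state, the SD and CV% would mix within-subject and between-subject variation, and n would count profiles rather than people.

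The clearance rule is a second, independent matter. After a single dose, the dose corresponds to AUC to infinity. At steady state it corresponds to AUC over one dosing interval. Extrapolating a steady-state profile to infinity adds drug left from earlier doses, so CL/F comes out too low, and Vz/F with it.

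**Working it through.** The SAP gives no figure to reproduce here, and Section 1.3 says that the sample size has no power basis. From the SAP: about 20 enrolled, at least 16 evaluable, three PK visits, twice-daily dosing (τ = 12 h), 10% extrapolation limit. Not in the SAP, so assumed: within-subject correlation ρ between visits, half-life, and absorption rate.

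**Records per cell.** 16 × 3 = 48 and 20 × 3 = 60, if every subject gives three complete profiles.

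**Pre-dose cell.** The Visit 1 pre-dose sample precedes any study drug and, if below quantitation, counts as zero. The Visit 2 and 3 pre-dose samples follow earlier doses. If their mean is T, the pooled mean is (0 + T + T)/3 = 2T/3, one third below the trough that it appears to report. This needs no assumed half-life or correlation.

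**SEM.** For three records per subject with equal variance σ² and correlation ρ, the variance of the pooled mean is σ²(1 + 2ρ)/(3n). Treating records as independent gives σ²/(3n). The SEM is therefore too small by sqrt(1 + 2ρ):

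| ρ (assumed) | factor | effective n of 48 | effective n of 60 |
|---|---|---|---|
| 0.3 | 1.26 | 30 | 37.5 |
| 0.5 | 1.41 | 24 | 30 |
| 0.7 | 1.55 | 20 | 25 |

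This takes the visit means as equal. If they differ, the pooled SD also absorbs the visit difference.

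**Location.** With one first-dose and two steady-state profiles, and steady-state exposure R times first-dose exposure, the pooled geometric mean is R^(2/3) times Visit 1 and R^(-1/3) times steady state. For R = 1.25 it is 16% above Visit 1 and 7% below steady state. For R = 0.8 it is 14% below and 8% above. Both values of R are illustrations.

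**CL/F at steady state.** One compartment, τ = 12 h, k = ln2/t½, f = exp(-kτ), absorption rate ka = 2 per h (assumed). Then AUC12h is proportional to 1 - k/ka, and the extrapolated part to f/(1 - f), with ka large enough that absorption is complete by 12 h. The relative bias of Dose/AUCinf against Dose/AUC12h is -[f/(1 - f)] / [(1 - k/ka) + f/(1 - f)].

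- t½ = 2 h: k/ka = 0.173, f = 0.0156, f/(1 - f) = 0.0159. Bias = -0.0159/0.8426 = -1.9%.
- t½ = 3 h: k/ka = 0.116, f = 0.0625, f/(1 - f) = 0.0667. Bias = -0.0667/0.9511 = -7.0%.
- t½ = 4 h: k/ka = 0.087, f = 0.125, f/(1 - f) = 0.1429. Bias = -0.1429/1.0562 = -13.5%.

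With instantaneous absorption the bias is simply -f: -1.6%, -6.25% and -12.5%. When the last quantifiable sample is at 12 h, the size of the bias equals the extrapolated fraction. The 10% rule therefore keeps the 2 h and 3 h cases and removes the 4 h case, so the bias in summarised values cannot much exceed 10%. The same rule takes longer half-life profiles out of the CL/F summary at Visits 2 and 3, where Dose/AUC12h would need nothing beyond 12 h.

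**The case against.** The best defence is that no sentence says that visits will be combined. Table 2 treats them as distinct, Section 4.1 speaks of visit-based summaries, and grouping by treatment in a one-arm study looks like template wording. Nominal sample time could be read as day plus hour. That stands in part: a reader might infer a decision to pool, and the text supports only an omitted stratum. But the day-plus-hour reading would split Visit 2, which floats from Day 2 to Day 4, and it cannot help the parameter summaries, which name no time dimension at all.

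It is also fair that the harm is bounded. The PK summaries are descriptive, with no interval, test or decision attached to the SEM. Concentrations and parameters are listed and individual profiles plotted, so tables by visit can be rebuilt. The correlations and half-lives above are assumed.

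On clearance, a reader who runs the same model at a half-life of 3.6 h obtains -10.9% and might report that as the error. It does not survive the SAP's own rule: in that model the profile has 10.9% extrapolated and is excluded from the summary. CL/F is also a secondary parameter, for the parent only, and the primary AUC12h, AUClast and Cmax do not depend on it.

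A reader might further infer that profiles taken after the PPI was stopped must be shown separately, since the SAP says "They may be weaned off PPIs during the study if medically appropriate", or that Visit 2 must be named the main profile. The documents do not compel either. Medication start and end dates are recorded and listed (Sections 3.5.2 and 4.2.4), so PPI status at a profile is recoverable. No comparison of early with full PPI effect is a stated objective. Section 2.1 announces four analysis sets and shows three, with text apparently removed, so it cannot be said that PPI status goes unhandled.

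**Conclusion.** The point holds and should be fixed, without being critical.

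The main part is the missing PK visit stratum in the summaries of a primary endpoint. Followed literally, Section 4.3 gives up to 48 to 60 records from 16 to 20 subjects, a pre-dose mean diluted by Visit 1 zeros, and an SEM too small by 1.26 to 1.55. That range assumes ρ of 0.3 to 0.7 and three complete profiles per subject.

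The smaller part is that Dose/AUCinf is the wrong quantity for steady-state CL/F, and Vz/F inherits the error. The bias is about -2% at an assumed half-life of 2 h and -7% at 3 h, and is capped near 10% in the summaries. The avoidable loss of longer half-life profiles from the CL/F summary is a further cost. This assumes that Visits 2 and 3 are in fact at steady state, as Table 2 intends.

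**What to change.** 1. In Section 4.3, summarise concentrations by analyte, PK visit and nominal time; draw the mean profiles by analyte and PK visit; and summarise parameters by analyte and PK visit. The cost is SAP wording and one more table dimension. The n per cell falls to at most 16 to 20, which is the true number of subjects.
2. In Section 3.1 and Table 4, keep CL/F = Dose/AUCinf for Visit 1. For Visits 2 and 3 define CL/F = Dose/AUC12h, and derive Vz/F as that CL/F divided by Kel. Table 4 has no row for AUC12h, although it is a primary parameter, so one is needed, including how it is obtained when the 12 h sample is below quantitation. Vz/F still depends on an acceptable Kel, so the existing Kel exclusions continue to apply to it.

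Neither change needs new data.

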4.4 Analysis of Efficacy

The efficacy analyses described in this section are secondary endpoints. Formal statistical analysis (with generation of a p-value) will not be performed for efficacy endpoints.

4.4.1 Alive and free of respiratory failure at Day 14 (and 28)

The first efficacy endpoint is the proportion of subjects who are alive and free of respiratory failure at Day 14, where respiratory failure is defined in Section 3.3.1.

The point estimate and its 90% confidence interval (CI; using Wald method with continuity correction) will be calculated and summarized. The difference in the proportion of subjects who are alive and free of respiratory failure at Day 14 with its 90% Cis will be included in this summary. The number and percentage of subjects who experienced respiratory failure but were free of respiratory failure at Day 14 will also be included in above summary.

For those wo have respiratory failure, summary statistics for the number of respiratory failures that occurred will be summarized.

This efficacy endpoint will also be summarized (point estimate and 90% CI Wald method with continuity correction as above) by the following subgroups:

• age (predefined age categories defined in Section 4.2.3)

- sex
- race
- ethnicity
- comorbidities (present vs absent)
- history of substance abuse (former/current/never)
- Concomitant antiviral use (yes vs no)
- Respiratory failure at baseline (with vs without, defined in Section 4.2.3)

The method for handling subjects that withdraw/ are lost to follow up prior to Day 14 is detailed in Section 3.3.1.

Similar analysis will be conducted for Day 28.

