1.3 Number of Subjects

Approximately 20 participants will be enrolled to have at least 16 evaluable participants. No formal power calculation is used for sample size determination. The sample size is chosen based on desire to gain adequate information while exposing as few patients as possible to the study procedure.

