2. ANALYSIS POPULATION

2.1 Definition of Analysis Set

Four analysis sets are defined in this study. A summary of the analysis sets used for each outcome variable in provided in Table 3.

The analysis populations are defined in Table.

Table 3 Populations for Analysis

Population/Analysis set	Description
PK Analysis Set (PKS)	The PK Analysis Set will include all participants who received ≥ 1 dose of
	acalabrutinib and had ≥ 1 post-dose evaluable PK data point for
	acalabrutinib. The population will be defined by AstraZeneca, the
	pharmacokinetics, and the statistician prior to any analyses being
	performed.
Safety Analysis Set (SAS)	The Safety Analysis Set will include all participants who received ≥ 1 dose
	of study intervention
Efficacy Evaluable Set (EES)	The Efficacy Evaluable Set will include all participants who received ≥ 1
	dose of study intervention

PK = pharmacokinetic;

; PPI = proton-pump inhibitor.

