3.3.1 Alive and free of respiratory failure at Day 14 (Day 28)

For the purpose of this study, respiratory failure is defined based on resource utilization of any of the following modalities:

- Endotracheal intubation and mechanical ventilation
- Oxygen delivered by high-flow nasal cannula (heated, humidified, oxygen delivered via reinforced nasal cannula at flow rates > 20 L/min with fraction of delivered oxygen ≥ 0.5)
- Noninvasive positive pressure ventilation or continuous positive airway pressure
- Extracorporeal membrane oxygenation

Only the subject's survival status and respiratory-failure status on Day 14 will be considered for this endpoint. If they experience respiratory failure after first dosed but recover by Day 14, per the definition above, they will be considered alive and free of respiratory failure at Day 14.

Subjects who are lost to follow up prior to Day 14, thus survival status and respiratory status at Day 14 cannot be assessed, will be included in the denominator of this analysis as though they had died or had a respiratory failure.

Similar analysis will be applied for alive and free of respiratory failure at Day 28.

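### The continuity-corrected Wald interval for the respiratory-failure endpoint is unreliable in small subgroups and near 0% or 100%, and can give limits outside 0–100%

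*SAP*

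**What the plan says.** Section 4.4.1 prescribes a "90% confidence interval (CI; using Wald method with continuity correction) will be calculated and summarized" for the Day 14 proportion and a similar analysis for Day 28. It then carries the method into subgroups: "This efficacy endpoint will also be summarized (point estimate and 90% CI Wald method with continuity correction as above) by the following subgroups". Eight factors follow. The first is "age (predefined age categories defined in Section 4.2.3"), and Section 4.2.3 lists six age bands alongside a split at 65 years.

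On size, Section 1.3 says "Approximately 20 participants will be enrolled to have at least 16 evaluable participants" and "No formal power calculation is used for sample size determination". Section 2.1 defines the denominator: "The Efficacy Evaluable Set will include all participants who received ≥ 1" dose. Under Section 3.3.1, subjects lost before the assessment "will be included in the denominator of this analysis as though they had died or had a respiratory failure", so losses do not shrink it.

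Section 4.4.1 gives no rule for truncating limits, no minimum subgroup size, and no exact or score alternative. Section 4.4 rules out p-values for efficacy.

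**The concern.** The Wald standard error is estimated from the observed proportion, so it is zero when nobody or everybody responds. All that remains is the continuity correction, and the interval is narrowest where the data say least about the upper or lower limit. In small cells such results are common, and the interval can also run past 0% or 100%.

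Because no p-values are planned, the interval carries the uncertainty statement for this endpoint. If a nominal 90% interval covers much less often than that, readers of a small preliminary-efficacy summary would take a few subjects as firmer evidence than they are, above all in the subgroup table.

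**Working it through.** The SAP gives no interval, expected proportion or power figure to reproduce, so the check evaluates the method it names.

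**Inputs.** Two-sided 90% level, z = 1.645 (Section 4.4.1). Full set n = 16 to 20 (Section 1.3). Subgroup size is not stated; six age bands over 20 subjects average 20/6 ≈ 3.3, so n = 3 to 5 is used as an assumption, with n = 10 for an even two-level split. The true proportion p is not stated and is varied from 0.05 to 0.95.

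**Formulas.** With p̂ = x/n, the corrected Wald limits are p̂ ± [1.645 × √(p̂(1 − p̂)/n) + 1/(2n)]. At x = 0 or x = n this is p̂ ± 1/(2n). Coverage at p is the sum of Binomial(n, p) probabilities over those x whose interval contains p.

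**Limits**

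| Result | Corrected Wald | Clopper-Pearson |
|---|---|---|
| 20/20 | 97.5% to 102.5% | 86.1% to 100% |
| 16/16 | 96.9% to 103.1% | 82.9% to 100% |
| 13/16 | 62.1% to 100.4% | 58.3% to 94.7% |
| 10/20 | 29.1% to 70.9% | 30.2% to 69.8% |
| 5/5 | 90.0% to 110.0% | 54.9% to 100% |
| 3/5 | 14.0% to 106.0% | 18.9% to 92.4% |
| 3/3 | 83.3% to 116.7% | 36.8% to 100% |

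For n = 16 to 20 a limit leaves 0–100% whenever x ≤ 3 or x ≥ n − 3. For n ≤ 5 it happens for every x.

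**Coverage, two cases by hand**

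- n = 3, p = 0.8. The intervals for x = 0, 1, 2, 3 are −16.7 to 16.7%, −28.1 to 94.8%, 5.2 to 128.1% and 83.3 to 116.7%. Only x = 1 and x = 2 contain 80%. Coverage = 3(0.8)(0.2²) + 3(0.8²)(0.2) = 0.096 + 0.384 = 48.0%.
- n = 20, p = 0.95. The interval at 20/20 starts at 97.5% and misses 95%; x = 16 to 19 contain it; 15/20 (56.6 to 93.4%) does not. The miss at 20/20 alone has probability 0.95²⁰ = 35.8%. Coverage is 63.9%.

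**Coverage of the nominal 90% corrected Wald interval**

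| n | Selected p | Mean over p = 0.1–0.9 |
|---|---|---|
| 3 | 48% at 0.2 or 0.8; 75% at 0.5 | 70% |
| 5 | 67% at 0.2 or 0.8; 80% at 0.3 or 0.7 | 76% |
| 10 | 65% at 0.1; at least 85% for 0.2–0.8 | – |
| 16 | 55.9% at 0.05 or 0.95; minimum 81% over 0.1–0.9 | 91% |
| 20 | 63.9% at 0.05 or 0.95; minimum 83% over 0.1–0.9 | 91% |

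**Alternatives.** Clopper-Pearson covers at least 90% throughout. Averaged over p = 0.1–0.9 it covers about 94–95% at n = 16 to 20 and 97–99% at n = 3 to 5. Wilson averages about 90% at n = 16 to 20, with a minimum of 83–84%, but covers only 75% at n = 3, p = 0.5.

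**The case against.** A reader might infer from the 56–64% figures that the interval fails generally at 16 to 20 subjects. The documents do not support that. Those figures need a true proportion near 5% or 95%; between 10% and 90% the corrected interval is close to nominal on average. At n = 20 it compares well with Wilson over that range: the minimum is 83.4% for both, and the mean is 91.2% against 90.2%. Nor does the SAP point to a proportion near 95%. Section 1 describes patients hospitalised for respiratory failure with a nasogastric tube in place, and Section 3.3.1 counts losses as failures; both pull the proportion down. A very low proportion would, however, bring the mirror-image problem, and the SAP rules out neither end.

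A reader might also infer that most subgroup cells will hold fewer than five subjects. The SAP gives no cell sizes. Several factors have two levels, where cells could be near 10 and coverage is tolerable in mid-range. The six age bands are the clearest place for very small cells.

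Finally, efficacy is secondary, descriptive and tied to no decision rule, and the counts and point estimates are unaffected.

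All of this limits the scope and weight of the point. It does not rescue the interval in cells of a few subjects or at results near 0% or 100%. Truncating the limits at 0 and 100% would remove the impossible values but leave coverage unchanged.

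**Conclusion.** The point holds with conditions. In subgroups of about 3 to 5 subjects the prescribed interval is unreliable: mean coverage is 70–76% against a stated 90%, 48% at n = 3 with p = 0.8, and a limit is always outside 0–100%. In the full set it is acceptable for true proportions of 10–90%, but coverage falls to 56–64% at 5% or 95%, limits are impossible whenever x ≤ 3 or x ≥ n − 3, and precision is false at 0/n and n/n. The arithmetic is exact. How often the bad cases arise rests on assumed subgroup sizes and an assumed true proportion. What is affected is the set of descriptive intervals on one secondary endpoint at two time points; no primary result is touched.

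**What to change.** In Section 4.4.1, replace the corrected Wald method with the Clopper-Pearson (exact) two-sided 90% interval for Days 14 and 28, overall and in every subgroup. Wilson would serve for the full set but is the weaker choice in very small cells. Suppressing intervals below some minimum cell size is a matter of preference and is not needed to correct the error.

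The change is one option in the frequency procedure, with no new data. Intervals become wider near 0% or 100% and are conservative on average. In mid-range nothing is lost: at 10/20 the exact interval is 69.8 − 30.2 = 39.6 points wide, against 70.9 − 29.1 = 41.8 for corrected Wald.

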3.5.2 Prior and Concomitant Medications and Procedures

All therapies (drug and non-drug), including herbal preparations, whether prescribed or over-the-counter, that are used during the study will be recorded on the eCRF. Details include generic and/or brand names of the medications, World Health Organisation Drug Dictionary (WHO-DD) encoding (B3 format), reason for use, route, dose, dosing frequency, and start and end dates. Procedures performed during the study will be recorded on the eCRF and details include the procedure name, WHO-DD encoding (B3 format), reason for the procedure, and start and end dates.

Prior therapies are defined as those taken prior to study treatment with a stop date prior to the first dose of study treatment. Concomitant therapies and procedures are defined as those with a stop date on or after the first dose date of study treatment.

Missing start and stop dates for medications and procedures will be handled using the rules described in Section 4.1.

Medications received prior to or concomitantly will be coded using the WHO Drug Dictionary Anatomical Therapeutic Chemical (ATC) classification codes. Concomitant medications will be summarized for the SAS by ATC classification codes. Subjects with the same concomitant medication/procedure multiple times will be counted once per medication/procedure. A medication/procedure that can be classified into more than one chemical and/or therapeutic subgroup will be presented in each subgroup.

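### The antiviral subgroup in SAP 4.4.1 has no time limit, so it can sort subjects partly by their course after first dose

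*SAP*

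**What the plan says.** SAP 4.4.1 gives the subgroup plan for the first efficacy endpoint: "This efficacy endpoint will also be summarized (point estimate and 90% CI Wald method with continuity correction as above) by the following subgroups". One of the eight factors is "Concomitant antiviral use (yes vs no". The section attaches no time window to it, and the Day 28 analysis is to follow the same plan.

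The term is defined only in SAP 3.5.2: "Concomitant therapies and procedures are defined as those with a stop date on or after the first dose date of study treatment". That rule looks at the stop date alone. It sets no latest start date and no cut at Day 14, Day 28 or last dose. The same section says of all therapies "that are used during the study will be recorded on the eCRF".

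The outcome is a status on a fixed day. SAP 3.3.1 states: "Only the subject's survival status and respiratory-failure status on Day 14 will be considered for this endpoint".

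The other factors are demographics, history or baseline status, and one says so in its name: "Respiratory failure at baseline (with vs without, defined in Section 4.2.3".

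**The concern.** A subgroup factor should be settled before the outcome it is used to stratify. Here it need not be. Two subjects who are alike at first dose can land in different subgroups because of what happened to them afterwards.

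This can happen in two ways. A subject who worsens or stays in hospital has more reason, and more days, to be given an antiviral. A subject who dies early, goes home early or is lost to follow-up has fewer days in which a start can occur or be recorded, and 3.3.1 counts those lost before Day 14 as failures. These routes do not all push the same way.

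For Day 14 there is a further oddity: a start on, say, Day 20 changes the subgroup in which an already fixed Day 14 result is counted.

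At stake is how the two rows of one prespecified table are read. A reader will compare yes with no, and the gap may reflect how the groups were formed rather than anything about antivirals.

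**Working it through.** The SAP gives no expected rate for this subgroup, so there is no figure to reproduce. The check has two parts.

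**1. Reading the rule.** Take a subject not on an antiviral at first dose.

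| Antiviral started | Stop date on or after first dose? | Subgroup under 3.5.2 | Known at first dose? |
|---|---|---|---|
| Never | – | No | – |
| Day 10, after worsening | Yes | Yes | No |
| Day 20, after the Day 14 assessment | Yes | Yes | No |

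Nothing else in the SAP narrows this.

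**2. Possible size.** Suppose antivirals have no effect at all. All four inputs below are assumptions; none comes from the SAP.

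- p: true proportion alive and free of respiratory failure
- b: share on an antiviral at first dose
- sF, sS: chance that a non-user starts one later, given failure or success

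Formulas:

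- Success rate in yes = [bp + (1−b)p·sS] / [bp + (1−b)p·sS + b(1−p) + (1−b)(1−p)·sF]
- Success rate in no = p(1−sS) / [p(1−sS) + (1−p)(1−sF)]

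Worked case, p = 0.50, b = 0.30, sF = 0.40, sS = 0.10:

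- Yes, successes: 0.15 + 0.35 × 0.10 = 0.185
- Yes, failures: 0.15 + 0.35 × 0.40 = 0.290
- Rate in yes: 0.185 / 0.475 = 38.9%
- Rate in no: 0.315 / (0.315 + 0.210) = 60.0%
- Gap: −21.1 points

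Other start rates, with p = 0.50 and b = 0.30:

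| sF | sS | Yes | No | Gap (points) |
|---|---|---|---|---|
| 0.20 | 0.05 | 43.2% | 54.3% | −11.1 |
| 0.30 | 0.10 | 42.0% | 56.3% | −14.2 |
| 0.50 | 0.10 | 36.3% | 64.3% | −28.0 |
| 0.60 | 0.10 | 33.9% | 69.2% | −35.3 |
| 0.10 | 0.40 | 61.1% | 40.0% | +21.1 |
| 0.20 | 0.20 | 50.0% | 50.0% | 0 |
| 0 | 0 | 50.0% | 50.0% | 0 |

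The sF/sS pairs 0.20/0.05, 0.40/0.10, 0.60/0.10 and 0.10/0.40 were also run with p at 0.3, 0.5 and 0.7 and b at 0.3 and 0.5. The gap stayed between about −35 and +21 points.

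If the subgroup is fixed by use at first dose, sF and sS drop out. Both rows then return p, and the gap is 0 under the same no-effect assumption.

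**Scale.** The planned 90% Wald interval with continuity correction at 5 of 10 is 0.50 ± (1.645 × √(0.25/10) + 1/20) = 0.50 ± 0.310, that is 19.0% to 81.0%.

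**The case against.** The case for leaving the text alone has four parts.

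- **Bias is possible, not shown.** A reader might infer that the subgroup estimates are biased, and biased against antivirals. The SAP does not support that. It gives no antiviral start rates, and what counts as best supportive care is normally a protocol matter. If no one starts late, or late starts are unrelated to outcome, the gap is zero. Early death can also make the yes group look better. This stands, and it limits the claim to *can be biased, direction unknown*.
- **Little depends on it.** SAP 1.3 says "Approximately 20 participants will be enrolled to have at least 16 evaluable participants. No formal power calculation is used for sample size determination", and SAP 4.4 says "Formal statistical analysis (with generation of a p-value) will not be performed for efficacy endpoints". No test or model of an antiviral effect is planned, and intervals as wide as 19% to 81% discourage close reading. This stands as to severity. It does not excuse the definition, because a wide interval shows imprecision and does not correct a bias.
- **Section 4.4.1 does not itself say that use is counted to the end of the study.** True. That follows from the open-ended rule in 3.5.2, but no other rule is available to the programmer.
- **A baseline definition does not make the comparison causal.** Also true: who is on an antiviral at first dose may depend on severity. It removes only the dependence on events after dosing.

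**Conclusion.** The point holds in a limited form. Followed as written, 4.4.1 with 3.5.2 counts antivirals started after first dose, including after the Day 14 assessment, so the subgroup can sort subjects partly by their later course. The Day 14 and Day 28 proportions in the two antiviral rows can then be biased. The sign and size cannot be found from the SAP; the range of about −35 to +21 points rests wholly on assumed values of p, b, sF and sS and on no antiviral effect.

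A reader might go further and take this as a flaw in the efficacy result. It is not. The overall Day 14 and Day 28 estimates do not use the antiviral flag, and neither do the primary pharmacokinetic and safety endpoints. No estimate of the effect of acalabrutinib is at issue. Severity is minor.

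**What to change.** Free improvement. In SAP 4.4.1, replace the subgroup with: *Antiviral use at baseline: started before, and not stopped before, the first dose of study drug (yes vs no)*. This wording leaves out courses that ended before first dose, which 3.5.2 treats as prior, and same-day starts after dosing.

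Add two sentences:

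- A start date imputed to the first-dose date under SAP 9.3 does not by itself count as baseline use. This is needed because 9.3 moves some missing or partial start dates to that day, for example when the day is missing and the month is that of first dose. A later start could otherwise pass as baseline use.
- Antivirals started after first dose are described separately in the concomitant medication summary (SAP 4.2.4), and not as an efficacy subgroup.

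The cost is a revised line in 4.4.1, the rule for imputed dates, and a split in one planned table. Start and end dates are already collected under 3.5.2, so no new data are needed.
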